#### **2. Précis/Abstract:**

Cytokines released by an activated immune system have been associated with decreased brain dopamine and the development of depression, which afflicts over 20 million adults in the United States. Biomarkers of inflammation, such as inflammatory cytokines and acute-phase proteins like C-reactive protein (CRP), are reliably elevated in a significant proportion of patients with mood and psychiatric disorders. Our recent findings using functional magnetic resonance imaging (fMRI) indicate that depressed patients with high inflammation (defined as plasma CRP  $>3$  mg/L) exhibit reduced connectivity between the striatum and prefrontal cortical brain regions, which associate with symptoms of reduced motivation or anhedonia, a core symptom of depression. The striatum is a key subcortical structure that sends and receives multiple projections to and from the frontal cortex and other brain regions to regulate motivation, and dopamine plays a key modulatory role. Therefore, inflammation-related decreases in striatal dopamine may influence corticostriatal connectivity to mediate symptoms of anhedonia. Our non-human primate work has revealed that inflammatory cytokine effects on striatal dopamine can be reversed by administration of the dopamine precursor, levodopa (L-DOPA). However, whether administration of L-DOPA in humans can reverse inflammation-related disruptions in corticostriatal connectivity and anhedonia is unknown. This study will test the hypothesis that administration of L-DOPA to depressed patients with high inflammation will 1) increase functional connectivity between the striatum and prefrontal cortical brain regions, and 2) improve objective measures of motivation compared to placebo. Medically healthy, medication free depressed patients will be recruited to ensure a range of inflammation from low to high (as determined by plasma CRP) and will undergo resting state fMRI before and after administration of low dose L-DOPA-carbidopa (250/50 mg) and placebo on separate, double blinded visits. This within subject, crossover design has been used previously in a similar study assessing the effects of L-DOPA on corticostriatal functional connectivity in healthy controls.(1) All subjects will undergo MRI scanning as well as neuropsychiatric assessments and blood sampling, when applicable, at baseline and before and after placebo or L-DOPA administration during 2 outpatient visits. This work will establish whether alterations in corticostriatal connectivity may serve as a sensitive and specific brain biomarker for the effects of inflammation on striatal dopamine, while providing supporting data for future studies exploring therapeutic strategies that facilitate availability of dopamine precursors in patients with anhedonia and increased inflammation.

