- antisocial personality disorder diagnosis as assessed during clinical interview, as well as a history of hospitalization and/or recurrent suicidal behavior judged to be directly due to the personality disorder
- Current eating disorder (aside from binge eating related to depression), unless otherwise approved by the principle investigator or PI's designee
- Current OCD, exclusionary only if impacting daily functioning, as assessed by clinical interview
- any other condition which in the opinion of the investigator would make the patient unsuitable for enrollment, or could interfere with participating in or completing the protocol
- smoking more than one half pack per day, or e-cigarette equivalent, unless otherwise approved by the PI or PI's designee

- initiation of any of the following medications, unless otherwise approved by the PI or PI's designee: Aspirin or Aspirin-like compounds (single dose within 48 hours), Ibuprofen or Naproxen Sodium (single dose within 48 hours), Cholesterol medications, Antibiotics, Herbal Medications, Psychiatric or Psychotropic Medications (including sedative hypnotics, anxiolytic medications or pain medications), Omega-3 supplements, Topical Steroids, Vaccinations (within the last 2 weeks)
- Currently on antidepressant medication, unless otherwise approved by the PI or PI's designee

**Urine drug screening:** A urine drug test (DrugCheck: NxScan Onsite Testcup or equivalent as approved by PI or designee) will be performed for every patient at screening and prior to each MRI scan. The urine test will allow for the qualitative detection of drug or drug metabolites in urine, including benzodiazepines, methamphetamine, cocaine, THC and morphine. Identification of a urine test positive for substance use will exclude the subject from participation, unless substance is a prescribed medication, or otherwise approved by PI or study physician.

**Urine Pregnancy Test:** A urine pregnancy test may be performed for women of childbearing potential if it has been >30 days since their last screening labwork (which includes a quantitative, serum hCG test). Identification of a positive urine pregnancy test will exclude the subject from participation.

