**Gender and Minorities:** Based on the composition of the patients treated for major depression at the Emory Clinic, Grady Health System, VAMC and community psychiatry clinics, we anticipate that an equal number of men and women will be included in the study. As for the racial composition of the sample, we anticipate 30-40% African Americans, 5-10% Latinos and 2-5% Asians, which is reflective of the community (city of Atlanta) from which our sample will be drawn.

**Dropouts:** Because participation in this study involves two screening visits followed within approximately 2 weeks by three study visits, we anticipate that there will be few subjects who will drop out between screening and the study visits. In our experience, however, there will be subjects who will have to be removed from the study because of a positive urine toxicology screen. In addition, some subjects may become too severely depressed and/or suicidal between enrollment and completion of the study. Given a conservative estimate of a 20% screen failures and 20% dropout rate, we will need to recruit ~ 225 subjects to reach the target of 80 subjects for analysis. Psychiatric staff is available throughout each subject's participation, and can provide on-site emergency care in the event of crisis.

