## **6. Participant selection**

Two hundred twenty-five depressed, medically stable males and females between the ages of 18 and 65 will be recruited for this study. All subjects (50% males and 50% females) will meet criteria for current major depression (MD). An equal number of participants will have CRP values from each of the three risk groups, as defined by CDC/AHA guidelines: <1mg/L (low), 1-3 mg/L (moderate), and >3mg/L (high). Based on retention rates in previous studies by our group utilizing a similar design in depressed subjects, we anticipate that recruiting 225 subjects will provide analyzable data for approximately 80 subjects. There will be no exclusions for race/ethnicity and minority populations and women will be actively recruited to ensure that 50% of the subjects will be female. We will make active attempts to enroll minority patients in a proportion that is reflective of the greater Atlanta metropolitan area from which patients will be recruited. No patients will be enrolled from vulnerable populations, including neonates, children, prisoners, or institutionalized individuals. No use will be made of fetal tissue. Patients will be obtained from multiple referral resources including the Emory Clinic, Grady Health System, the Veterans Administration Medical Center (VAMC), and community psychiatrists. In addition, subjects will be obtained from ongoing clinical trials including the Mental Health Centers for Intervention Development and Applied Research (CIDAR) trial, which is scheduled to enroll 400 subjects over 5 years. Depressed subjects will also be obtained from newspaper and radio advertisements as well as internet solicitation. Subjects in this study may also be referred from our Behavioral Immunology Program "Recruitment Clinic" protocol, Clinical Research in Psychiatry: IRB0000075162, which uses the screening strategy similar to this protocol to recruit and screen patients with depression for our active studies through IRB approved social media campaigns. Subjects who are determined to be eligible for this study will be referred to study staff. Participants who have consented to any Emory Behavioral Immunology Program studies will be given an option to consent to have any screening and study data used in future studies, including this study. If the participant consents to this option, any previously completed screening or study assessments may be used

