in the current study to help reduce patient burden. Some labs or evaluations may be repeated at the discretion of the PI or PI's designee, if more current data is needed. We anticipate that at least 2 subjects per month (~24 subjects per year) will consent to enter this study. This estimate is based on ongoing projects that have been recruiting subjects for related studies over the past 5 years. Of subjects who meet entry criteria, our past experience suggests that approximately 20% will discontinue study participation.

Patients with MD enrolled in the study will meet DSM-V-TR criteria for a current major depressive episode without psychosis with a symptom severity score of  $\geq 18$  on the Hamilton Depression Rating Scale (HDRS) -17 item scale. To be included, subjects must not demonstrate active suicidal intent or plan and must score  $\leq 2$  on the HDRS or QIDS suicide item, and must have no suicide attempt within six months of screening. Enrolled subjects will have no history of the following: schizophrenia, schizoaffective disorder, other (non-mood disorder) psychosis, depression secondary to a medical condition, mental retardation, and substance dependence [or abuse within the past year (except nicotine)], dementia or MMSE  $<28$ , unless otherwise approved by the PI or PI's designee, or delirium. Subjects will be at risk for exclusion for a urine toxicology screen positive for ETOH or drugs of abuse. The presence of post-traumatic stress disorder, panic disorder, obsessive compulsive disorder or social phobia will not disqualify subjects from enrollment as long as depression is the primary diagnosis, though post-traumatic stress disorder may be considered as a covariate in statistical analyses. Enrolled subjects may have a comorbid personality disorder; however, subjects who meet criteria in clinical interview for antisocial personality disorder will be disqualified, as will subjects with a history of hospitalization and/or recurrent suicidal behavior judged to be directly due to the personality disorder.

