## 7. Statistical Analysis

**Power Analysis:** To ensure a range of inflammation from low to high, we will analyze an equal number of participants from low to high inflammation levels: approximately 27 patients with CRP  $<1$ mg/L, 27 patients with CRP 1-3mg/L, and 27 patients with CRP  $>3$ mg/L. We recently completed a study using a similar enrollment strategy and analyzed data from ~80 medication-free subjects over a similar time frame. Based on our preliminary data, we anticipate large effect sizes (Cohen's dz  $\sim 1$ ) for L-DOPA-induced increases in connectivity in patients with high inflammation; thus with n=30 per group we will have  $>80\%$  power at  $\alpha=0.05$ .

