### **Analysis Plan and Statistical Methods:**

Descriptive statistics will be used to describe the central tendencies and variances of dependent variables and demographic and clinical characteristics of the patients. Due to the pilot nature of this project, we will use both targeted and exploratory data analysis methods to determine whether L-DOPA increases corticostriatal connectivity in depressed patient with high versus low inflammation. Statistical modeling will be conducted as described below. Log-transformation will be used for non-normally distributed data. Statistics will be two-tailed with alpha <0.05, and conducted in SAS and SPSS.

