**Analytic Strategy, Objective 1:** The primary outcome will consist of a targeted, hypothesis-driven approach including extraction of individual patient level Z scores for connectivity with ventral or dorsal striatum and regions of interest identified in our previous work that 1) exhibited alterations in connectivity between patients with high and low inflammation, and 2) were significantly associated with behaviors of interest. Post-L-DOPA or placebo administration Z scores will be entered into linear models controlling for pre-administration connectivity scores as well as relevant covariates. The difference (delta; post minus pre) in connectivity Z scores before and after placebo and L-DOPA will also be compared by paired T test, and between patients with high and low inflammation (CRP > or < 3mg/L). Generalized linear mixed model (GLMM) will be used to assess whether corticostriatal connectivity is improved by L-DOPA, and whether effects depend on concentrations of CRP, while controlling for clinical and demographic covariates. Linear regression models will be used to determine whether increased CRP is associated with decreased response to hedonic reward, as assed at by fMRI using the MIDT. Response to hedonic reward (as measured by MIDT) will also be used to assist in interpretation of resting-state connectivity data before and after L-DOPA administration in two ways: 1) Striatal regions activated in response to reward will be used to corroborate location of the striatal seed regions for resting-state connectivity analysis, and 2) responses to the MIDT will be entered into GLMM models to determine whether decreased reward sensitivity predicts greater increase in connectivity after L-DOPA. White matter integrity as measured by DTI will also be used to assist in interpretation of responses to L-DOPA, as subjects with less cortical-striatal-thalamic anatomical connections may have less ability to respond to increases in dopamine. To identify other corticostriatal circuits that may be affected by increasing dopamine precursor, striatal seed-to-whole-brain comparisons of L-DOPA versus placebo, will be performed as a secondary analysis strategy. In the event that CRP fails as a classification or correlational variable, exploratory analyses will be conducted using other measures of inflammation described above for Objective 1.

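### The planned paired t test uses only patients with all four scans and ignores period, and the plan does not say whether one-visit patients enter the mixed model

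*Combined protocol and SAP*

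**What the plan says.** The Précis describes a within-subject crossover with scans "before and after administration of low dose L-DOPA-carbidopa (250/50 mg) and placebo on separate, double blinded visits". Each patient therefore has up to four resting-state scans.

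Section 7, Analytic Strategy, Objective 1, lists three analyses of the connectivity scores:
- linear models of post-dose scores, adjusted for the pre-dose score and relevant covariates;
- the paired comparison: "The difference (delta; post minus pre) in connectivity Z scores before and after placebo and L-DOPA will also be compared by paired T test";
- a GLMM for whether L-DOPA improves connectivity and whether the effect depends on CRP, adjusted for clinical and demographic covariates.

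No section defines the analysis set, an incomplete pair, a missing-data method, or a period or sequence term. None says which of the three analyses decides the question.

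Several provisions can leave a patient with fewer than four scans. Urine screening is repeated before each MRI, and "Identification of a urine test positive for substance use will exclude the subject from participation", subject to exceptions. The Dropouts paragraph of section 5 expects that "there will be subjects who will have to be removed from the study because of a positive urine toxicology screen", and that some patients may become too depressed or suicidal before completing. A scan is terminated if claustrophobia develops (MRI Neuroimaging). Adverse events, withdrawal and loss to follow-up end participation (Interim Monitoring and Early Stopping).

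On amount, section 6 says that, of those meeting entry criteria, "approximately 20% will discontinue study participation", and that recruiting 225 "will provide analyzable data for approximately 80 subjects".

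**The concern.** The paired test drops anyone with one completed visit, including a valid randomised visit-1 result. If loss after visit 1 were unrelated to drug and outcome, the cost would be a little precision. If it depends on the drug just taken and on how the patient did, the completers' values under that drug are selected, and the paired mean can be shifted even with no drug effect. Section 10 calls nausea and vomiting frequent with levodopa, so a link between first drug and leaving is plausible, though not shown.

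Separately, unequal loss between the two sequences unbalances the crossover. Part of any visit-1 to visit-2 change then enters the simple paired mean, because the test has no period term. A mixed model that keeps visit-1 data and includes period addresses both problems, but the plan does not say that its GLMM does either.

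**Working it through.** **1. The plan's own power figure.** Inputs from section 7: "we anticipate large effect sizes (Cohen's dz" about 1), n = 30 per group, and "Statistics will be two-tailed with alpha <0.05, and conducted in SAS and SPSS". Exact paired-t power is 99.96% at n = 30, and 99.88% at the 27 per CRP group named in the same paragraph. The stated >80% is therefore true with a wide margin; about 10 complete pairs already give 80%. If, as a test case only, 20% of each group lacked a complete pair, power at dz = 1 would be 99.7% (n = 24) or 99.4% (n = 22). Any problem is bias, not power at this effect size.

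**2. Can the share lost after the first dose be worked out?** No. The Dropouts paragraph gives 20% screen failure and 20% dropout, but 225 × 0.8 × 0.8 = 144, not 80, and 80/225 = 35.6% overall retention. Nothing splits the 20% by visit.

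**3. Period effect carried into the paired mean.** With completers n_L (L-DOPA first) and n_P (placebo first), the share carried is (n_P − n_L)/(n_P + n_L). Assume 50 per sequence and 20% loss overall:

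| Loss, L-DOPA first / placebo first | n_L, n_P | Share of period effect carried |
|---|---|---|
| 20% / 20% | 40, 40 | 0 |
| 25% / 15% | 37.5, 42.5 | 5/80 = 0.06 |
| 30% / 10% | 35, 45 | 10/80 = 0.125 |
| 40% / 0% | 30, 50 | 20/80 = 0.25 |

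**4. Outcome-related loss, no drug effect and no period effect.** Assumptions: visit-level change scores have SD 1 and between-visit correlation r; 30% of L-DOPA-first patients are lost, loss having (latent normal) correlation c with a low visit-1 result; 10% of placebo-first patients are lost at random.
- Mean visit-1 shift in retained L-DOPA-first patients: c × 0.3477/0.7 = 0.497c (0.3477 is the normal density at the 30% point).
- Their visit-2 values shift by r times that, so their paired difference shifts by 0.497c(1 − r).
- They are 35 of 80 completers, so bias = 0.4375 × 0.497c(1 − r) = 0.217c(1 − r).
- Standard error is √(2(1 − r)/80): 0.132, 0.112 and 0.087 at r = 0.3, 0.5 and 0.7. The false-positive rate follows from bias/SE and the normal distribution.

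| c | Bias (SD) at r = 0.3 / 0.5 / 0.7 | False positives |
|---|---|---|
| 0.3 | 0.046 / 0.033 / 0.020 | about 6%, near nominal |
| 0.5 | 0.076 / 0.054 / 0.033 | about 9 / 8 / 7% |
| 0.8 | 0.122 / 0.087 / 0.052 | about 15 / 12 / 9% |

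Simulations of the same set-up agree, ranging from 0.01–0.05 SD with near-nominal error at c = 0.3 to 0.05–0.13 SD with 8–16% error at c = 0.8. With half the loss (16%/4%, c = 0.8), bias is 0.07 / 0.05 / 0.03 SD and error 7–9%. With 10%/5% loss and c = 0.3, bias is at most 0.02 SD and error about nominal.

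**5. The alternative.** In the same simulations, a generalized least squares model with drug and period that keeps one-visit patients has bias under 0.01 SD and 4–6% error. This is partly by construction: loss depends only on the observed visit-1 value, and the model is given the true covariance.

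**The case against.** The paired test is neither the only nor the leading analysis. It is introduced as an addition, and the question of whether L-DOPA improves connectivity is given to the GLMM, which can use one-visit patients. That stands: the plan is not committed to completers only. What is missing is a statement that such patients enter, and a period term.

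Stronger readings are tempting, but the documents do not support them:
- A reader might infer that about 20% drop out of the paired test. The 20% covers all discontinuation among those meeting entry criteria, its timing is not given, and the 80 is already net of loss.
- A reader might infer bias towards L-DOPA. That requires poor connectivity responders to leave after L-DOPA. Nothing links connectivity change to leaving, and the opposite link reverses the sign. Connectivity is extracted from scans later and is not something a patient perceives, so a correlation as high as 0.8 is near a worst case.
- A reader might infer that a later positive urine screen deletes visit-1 data. The rule concerns participation and allows exceptions; it says nothing about data already collected.
- A reader might count every stopped scan as a lost pair. Removal during a task need not lose the resting-state scan, because the order of sequences is not given.

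Section 10 also says that carbidopa reduces nausea and vomiting and describes the acute effects at study doses as transient and mild, which weakens the drug-related route without closing it. The study also describes itself as a pilot.

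**Conclusion.** The concern holds as a modest safeguard against bias, with some gain in precision. The paired test as written drops one-visit patients and ignores period, and the plan does not say that its GLMM does otherwise. The fraction affected cannot be derived from the documents.

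Under the assumed 30%/10% loss by sequence, 100 patients and between-visit correlation 0.3 to 0.7, completers' bias is about 0.01–0.05 SD with near-nominal error at weak dependence (0.3), and about 0.05–0.13 SD with 8–16% error at strong dependence (0.8). Smaller loss gives smaller figures. In the splits shown, up to a quarter of any period effect would also enter the paired mean. Loss rates, dependence and direction are all assumptions, so the figures should be read as a range and not as a forecast.

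**What to change.** In section 7, Analytic Strategy, Objective 1:
- Make the GLMM the main L-DOPA versus placebo comparison. Include every randomised patient with at least one completed pre/post pair, analysed under the drug assigned at that visit, with patient as a random effect and drug and period as fixed effects alongside the planned covariates.
- Label the paired t test a completers' sensitivity analysis.
- State that valid visit-1 data are kept for patients removed before visit 2. This concerns data handling only and leaves the removal rules as they are.
- Report the number lost after visit 1 by drug received, with reasons. The annual DSMB report in section 9 already counts post-randomisation dropouts and their reasons.

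The cost is a few sentences and slightly more analysis work, with no new data. The model relies on missing-at-random, and it does not recover a visit whose own post-dose scan was aborted; those visits should be counted and reported. If loss proves to be purely random, the gain is small (standard error 2–4% lower in simulation).
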